8.5 Interim Analysis

The most current version of PASS software Using PASS 2022 (Power Analysis and Sample Size Software (2022). NCSS, LLC. Kaysville, Utah, USA, ncss.com/software/pass) was used to estimate conditional power at $n=46$. It was determined that at $n=46$, a power of 80.65% could detect a mean difference of 7, with a non-inferiority margin of 0.5, at a target alpha-level of 0.05. The assumed population means are 40 and 33, with known standard deviations of 10 and 10. These results are based on one-sided t-test group sequential testing with 3 stages and boundary values calculated from spending functions. Since it is expected that 80% power has been achieved with $n=46$ cases, it is a reasonable time to perform in interim analysis to test for early efficacy and/or futility.

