8 STATISTICAL CONSIDERATIONS

8.1 Sample Size Determination

A previous pilot study was conducted using a within-subjects design, applying both of the dressings described herein to two different wounds on the same subject, measuring wound reduction and other variables. In that study, the MPS dressing that was used led to a 40% reduction in wound size, whereas the CMS dressing led to a 33% reduction.¹¹ The data was used to determine the appropriate sample size for this study.

A power analysis using G*Power 3.1 for an independent samples t-test indicated that with the above reduction in wound sizes and a 10% standard deviation for each treatment, 68 subjects would be necessary to attain 80% power at a two-tailed alpha of 0.05, assuming a 1:1 assignment to the two dressing groups. A target of 80 subjects will be used in order to account for subjects' lost-to-follow-up and other scenarios that result in incomplete data.

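### Section 8.5 justifies the look at 46 subjects by 80% power, but that figure belongs to a one-sided test with a 0.5 margin; the two-tailed test of 8.1 has at most 64.1% power there

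*Combined protocol and SAP*

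**What the plan says.** Section 8.1 (Sample Size Determination) uses an independent-samples t-test with mean wound-size reductions of 40% and 33% and SD 10% in each arm. It concludes that "68 subjects would be necessary to attain 80% power at a two-tailed alpha of 0.05, assuming a 1:1 assignment to the two dressing groups". Enrolment is then raised: "A target of 80 subjects will be used in order to account for" losses and incomplete data.

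Section 8.5 (Interim Analysis) starts from the same effect: "The assumed population means are 40 and 33, with known standard deviations of 10 and 10". It says PASS "was used to estimate conditional power at" 46 subjects and that "a power of 80.65% could detect a mean difference of 7, with a non-inferiority margin of 0.5, at a target alpha-level of 0.05". The method is described in one sentence: "These results are based on one-sided t-test group sequential testing with 3 stages and boundary values calculated from spending functions". From this the section infers that "it is expected that 80% power has been achieved" at 46, and therefore that "it is a reasonable time to perform in interim analysis to test for early efficacy and/or futility".

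Non-inferiority appears nowhere else in the document. The Synopsis (1.1), Background (2.1) and Overall Design (4.1) all ask which of the two dressings is better. Sections 8.2 and 8.4 refer to a separate SAP that is still to come; it is not part of this file.

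**The concern.** The same means and SDs cannot need 68 subjects for 80% power in one section and 46 in another unless the test has changed. It has: 8.5 is one-sided at 0.05 rather than two-tailed, and it adds a non-inferiority margin of 0.5. The resulting power is then used as if it belonged to the trial's own superiority question.

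This matters because the look may end the trial. Someone who believes that 80% power has been reached at 46 will read a non-significant or futile result there as stronger evidence of no difference than it is. On the efficacy side, 8.5 does not say whether crossing its boundary would show superiority or only non-inferiority at one-sided 0.05, which is a weaker claim than the one 8.1 is sized for.

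Two smaller points go with it. Conditional power is the wrong term, because no interim data enter the calculation. The section also speaks of three stages and spending functions but describes a single look, and it names no function, look sizes, futility rule or final alpha.

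**Working it through.** **Inputs.** Difference 40 − 33 = 7 and SD 10 per arm (8.1 and 8.5); 1:1 allocation (8.1); two-tailed 0.05 (8.1); one-sided, alpha 0.05, margin 0.5, n = 46 (8.5). The 46 is taken as a total, 23 per arm: 46 per arm would be 92 subjects, more than the target of 80.

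**Formula.** For n per arm, SE = 10 × √(2/n), noncentrality = distance / SE, df = 2n − 2. Power is the probability that a noncentral t with these values exceeds the critical t. At n = 23, SE = 10 × √(2/23) = 2.949 and df = 44.

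**Step 1: reproduce the plan's figures.**
- 8.5, margin added: distance 7 + 0.5 = 7.5, noncentrality 7.5/2.949 = 2.543, one-sided critical t 1.680. Power 80.5%. A three-stage one-sided O'Brien-Fleming-type design with equally spaced looks, ending at 46, gives about 80.8% (known SD). Both agree with 80.65%.
- 8.5, margin subtracted: distance 6.5 gives 70.0%. Pocock-type spending with the margin added gives 75.6%. Neither matches.
- 8.1: 33 per arm gives 79.97% and 34 per arm gives 81.2%, so N = 68 is right.

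**Step 2: change one element at a time at 46 subjects.**

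| Test at 23 per arm | Distance | Critical t | Power |
|---|---|---|---|
| One-sided 0.05, margin added (8.5) | 7.5 | 1.680 | 80.5% |
| One-sided 0.05, no margin | 7 | 1.680 | 75.6% |
| Two-sided 0.05, no margin (8.1) | 7 | 2.015 | 64.1% |

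The 8.1 test reaches 81.2% at 68 and 87.1% at 80. The 64.1% assumes that all the alpha is used at 46. Any plan that keeps some for the final analysis has less.

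**Step 3: what an interim at 46 can deliver.** Here one interim look precedes the final, under two-sided 0.05 spending. The boundaries come from the bivariate normal with correlation √(46/N), and the crossing probabilities from the noncentral t.

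| Spending, final N | p at 46 | p at final | Chance of crossing at 46 |
|---|---|---|---|
| O'Brien-Fleming-type, 68 | 0.0129 | 0.0461 | 42% |
| O'Brien-Fleming-type, 80 | 0.0062 | 0.0480 | 32% |
| Pocock-type, 68 | 0.0386 | 0.0246 | 60% |
| Pocock-type, 80 | 0.0344 | 0.0262 | 58% |

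With SD 10, the O'Brien-Fleming-type boundary at 46 needs an observed difference of about 2.592 × 2.949 = 7.6 (N 68) or 2.875 × 2.949 = 8.5 (N 80). Both exceed the planned 7.

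**Step 4: what a null result at 46 means.** If the planned effect is real, the 8.1 test is non-significant at 46 in 1 − 0.641 = 35.9% of trials. The stated power implies 1 − 0.8065 = 19.4%. In simulation (1,000,000 trials per case), 52% of those non-significant trials would be significant at a final N of 68, and 67% at 80, using the adjusted O'Brien-Fleming-type final level.

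**Step 5: two illustrations under assumed rules.** The documents state neither rule.
- If any two-sided p > 0.05 at 46 stopped the trial, power would fall from about 80.7% to 62% (N 68) or from 86.9% to 63% (N 80).
- If a one-sided, margin-based O'Brien-Fleming-type boundary at 46 were followed by an unadjusted two-sided 0.05 final test, and crossing were read as superiority, the overall false-positive rate would be about 6.4% (N 68) or 5.8% (N 80).

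**The case against.** The 80.65% is not a miscalculation. It is about right for the test that 8.5 openly describes, with sidedness, margin and alpha all stated. The defect is an inconsistency of hypothesis rather than a wrong sum. That is correct, but the section goes on to use the figure as the reason for the look, and for the trial's own question that reason is false.

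Section 8.5 assumes known SDs, and a known-SD calculation gives 66.0% rather than 64.1%. Both sections name a t-test, however, so 64.1% is the relevant ceiling, and two points would not rescue an 80% claim.

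The harm requires an early stop, and no stated rule stops the trial on a non-significant result at 46. This stands. The losses in Step 5 are illustrations, not properties of the written plan. The spending function, look sizes, futility rule and final alpha may also be in the SAP that is not in this file, so their absence here is only missing detail and does not carry the conclusion.

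The example boundaries assume one interim look, whereas 8.5 mentions three stages, and 46 is close to two-thirds of 68. The N = 80 figures treat all 80 as evaluable, although 8.1 makes 80 an allowance for incomplete data. Both limits stand, and they bear on the examples rather than on the 64.1%.

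**Conclusion.** The concern holds with high confidence, and 8.5 should be corrected before the look is taken. On the plan's own inputs (difference 7, SD 10, 23 per arm), the test that sizes the trial has at most 64.1% power at 46, not 80.65%, and first reaches 80% at 68 subjects with equal arms. Of the gap of about 16 points, the margin accounts for about 5 (80.5% to 75.6%) and the switch to a one-sided test for about 11 (75.6% to 64.1%).

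A look at 46 is not wrong in itself, and the final analysis is sound if the trial continues under a proper spending plan. What fails is the stated reason for a look that can end the trial. These documents do not show whether the overall false-positive rate is controlled. The 64.1% rests only on the plan's effect size, SD and allocation, and on reading 46 as a total.

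**What to change.** In section 8.5:

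1. Use the two-sided superiority hypothesis of 8.1 at the interim. Delete the 0.5 margin, the term conditional power, and the statement that 80% power has been reached. If the sponsor does intend a non-inferiority claim, it must be stated as a trial hypothesis and reconciled with 1.1, 2.1, 4.1 and 8.1.
2. Replace 80.65% with the probability of crossing the chosen efficacy boundary at 46, for example about 42% (final N 68) or 32% (final N 80) under O'Brien-Fleming-type spending, and note that fixed-sample power there is 64%.
3. Put the interim and final analyses under one two-sided 0.05 spending plan with a named function, all look sizes (reconciling three stages with the single look described), a final alpha and a non-binding futility rule. If the SAP already holds these items, cite it in 8.5.

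The spending function is the sponsor's choice. As an example for one interim with O'Brien-Fleming-type spending: p ≤ 0.0129 at 46 and p ≤ 0.0461 at 68, or p ≤ 0.0062 and p ≤ 0.0480 if the final N is 80. These values change if three looks are meant.

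The cost is wording, with no extra subjects. O'Brien-Fleming-type spending takes final power from 81.2% to about 80.7% at 68, or from 87.1% to about 86.9% at 80. Pocock-type spending costs more, leaving about 76% and 83%. The interim figure that the plan can report becomes less favourable.

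### The 80.65% power that Section 8.5 gives at n=46 needs essentially the whole one-sided 0.05 by that point, so it does not describe an interim look in the 68- or 80-subject trial of Section 8.1

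*Combined protocol and SAP*

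**What the plan says.** Protocol Section 8.1 sizes the trial with an independent-samples t-test: reductions of 40% and 33%, SD 10 in each arm, 1:1 allocation. It concludes that "68 subjects would be necessary to attain 80% power at a two-tailed alpha of 0.05", and raises the target to 80 to allow for incomplete data.

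Section 8.5 adds an interim analysis. It claims for 46 subjects that "a power of 80.65% could detect a mean difference of 7". The inputs listed there are a target alpha of 0.05, a margin of 0.5 for non-inferiority, the same means and known SDs of 10. The method is a one-sided t-test under "group sequential testing with 3 stages", using boundaries derived from spending functions. Because 80% power is expected to be reached at 46 cases, it concludes that "it is a reasonable time to perform in interim analysis to test for early efficacy and/or futility".

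The section does not give the sizes of the three stages, the spending function, the alpha spent at n=46, or the alpha left for the final test. Section 8.4 defers details of statistical testing to a forthcoming SAP.

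**The concern.** The two sections differ in sidedness (one-sided against two-sided), hypothesis (margin 0.5 against no margin), number of analyses (three stages computed, one look described) and final size (46 against 68 or 80). Power near 80% with only 46 of 68 or 80 subjects suggests a calculation in which 46 is the end of testing, not an intermediate point.

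Two things are at stake. The reason given for looking at n=46 may be untrue for this trial. And if a one-sided 0.05 is used at 46 and a two-sided 0.05 is used again at the end, the false-positive rate exceeds 5% on the primary comparison of an open-label trial.

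**Working it through.** **Inputs.** From Section 8.5: n=46, read as 23 per arm because 46 per arm would be 92, above the target of 80; difference 7; margin 0.5, so distance from the null 7 + 0.5 = 7.5; SD 10; one-sided 0.05. From Section 8.1: N=68 or 80, two-sided 0.05, 1:1 allocation.

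**1. Main sample size.** SE = 10·√(2/34) = 2.425, noncentrality 7/2.425 = 2.89, 66 df. Two-sided t power is 81.2%, so 68 is confirmed.

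**2. The 80.65%.** SE at 23 per arm = 10·√(2/23) = 2.949, and 7.5/2.949 = 2.543.
- Single fixed one-sided 0.05 test: Φ(2.543 − 1.645) = 81.6% (z), or 80.5% (t).
- Last of three equal stages, known SD: 80.9% with O'Brien-Fleming-type spending 2[1 − Φ(1.960/√t)]. Other families give 80.1% (t²), 80.9% (t³) and 81.1% (Hwang-Shih-DeCani −4). Pocock-type (75.6%) and linear (77.5%) spending do not match. Simulated t-versions of the O'Brien-Fleming, t³ and Hwang-Shih-DeCani designs give 79.7% to 80.0%.
- Backwards: 80.65% needs a critical value of 2.543 − 0.865 = 1.678, a one-sided alpha of 0.0466 (z) or 0.0506 (t). That is essentially the whole 0.05.

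**3. If n=46 is a true second look of three (looks at 23, 46 and N; one-sided 0.05; distance 7.5).**

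| Final N | Spending | Alpha spent by 46 | Power by 46 |
|---|---|---|---|
| 68 | O'Brien-Fleming-type | 0.0172 | 66.4% |
| 68 | Pocock-type | 0.0386 | 73.7% |
| 80 | O'Brien-Fleming-type | 0.0097 | 58.1% |
| 80 | Pocock-type | 0.0344 | 72.1% |

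With only one interim look, the highest value found is 78.1% (Pocock-type, N=68).

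**4. Power at n=46 for the Section 8.1 test.** Noncentrality 7/2.949 = 2.374, 44 df, two-sided 0.05: 64.1%. One-sided 0.05 without the margin gives 75.6%.

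**5. Type I error if both tests are run at their stated levels.** The two test statistics have correlation √(46/68) = 0.822 or √(46/80) = 0.758.
- Favourable direction, P(Z₁ > 1.645 or Z₂ > 1.960): 5.8% (N=68) or 6.1% (N=80).
- Adding the lower 2.5% of the final test: 8.3% or 8.6%. Mixed sidedness alone accounts for 5% + 2.5% = 7.5%, so repeat testing adds 0.8 or 1.1 points.
- Two-sided 0.05 at both analyses: 7.7% or 8.0%.

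**The case against.** The strongest defence is that Section 8.5 mentions spending functions and Section 8.4 leaves test details to the SAP. On that view the 0.05 in Section 8.1 is only a sample-size input, and nothing says that the look will be unadjusted or that the final test keeps its full alpha. This stands as far as it goes: the error rates in step 5 are conditional. It does not rescue the power statement, which is already made as a fact and as the reason for the look.

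A reader might also infer that n=46 is shown to be the third and last stage, leaving no alpha for the final test. The documents do not support that. They give no stage sizes, and a single fixed test reproduces the figure about as well as the three-stage model. Some designs ending at 68 also have overall power near 80.65%, for example distance 6.5 with Pocock-type or linear spending. They reach it at 68, however, and the text places it at 46.

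Finally, adding the 0.5 margin at the look would take the total error to 10.1% to 10.4%, but only if a non-inferiority rejection were reported as superiority. At a true difference of 0 the non-inferiority null is false, so rejecting it is not in itself an error, and Section 8.5 does not say it would be reported as superiority.

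**Conclusion.** The concern holds in a limited form. The stated power at n=46 needs essentially all of a one-sided 0.05 by that point; the stage structure behind it is an inference. For the planned trial, the claim that 80% power is reached at 46 does not hold: it is 64.1% for the Section 8.1 test, and about 58% to 74% for the Section 8.5 test as a second look of three with O'Brien-Fleming- or Pocock-type spending. This is a conflict between stated figures, not merely missing detail.

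The inflation to 8.3% to 8.6% should not be read as what the trial will do. It assumes that both tests are run at the only levels stated, and most of it is mixed sidedness rather than exhausted alpha. All figures assume 23 per arm at the look, SD 10 and a true difference of 7 for power. The type I error figures use the normal approximation.

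**What to change.** Rewrite Section 8.5, and carry it into the SAP before any look, for the Section 8.1 hypothesis: two-sided overall 0.05, no margin, one stated maximum N (68 or 80 evaluable) as the last analysis, a named spending function, and alpha shared between the n=46 look and the final test.

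One reasonable option is two analyses with O'Brien-Fleming-type spending and non-binding futility:
- N=68 (information 46/68 = 0.676): p<0.0129 at 46, p<0.0461 at the end.
- N=80 (information 46/80 = 0.575): p<0.0062 at 46, p<0.0480 at the end.

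A three-stage design would also serve if its stage sizes and boundaries are stated and its last stage is the maximum N. Delete the 80.65% and the claim that 80% power is reached at 46, or restate the power at the look.

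The cost is mainly rewording. For N=68, t-based overall power falls from 81.2% to about 80.7%. The chance of stopping for efficacy at 46, under the assumed difference of 7, is about 42% (N=68) or 32% (N=80), and the protocol should say so.

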9 SUPPORTING DOCUMENTATION AND OPERATIONAL CONSIDERATIONS

9.1 Clinical Monitoring

The Clinical Research Associate (CRA) will confirm that the rights and well-being of subjects are protected, and that the reported trial data are accurate, complete, and verifiable from source documents. Moreover, the CRA will confirm the conduct of the trial by the PI, sub-investigator(s), and sites are in compliance with the protocol, GCP, and regulatory requirements as well as any applicable institution or IRB and federal or local processes. Monitoring will occur at minimum every two months, or more or less, depending on the enrollment during the study duration. It will occur more frequently if:

- The volume of data is large, there is a backlog of data to review due to unexpected issues, or there are quality issues with the data
- The site compliance with the protocol or compliance with expected ICH/GCP and regulatory requirements is lacking or there are continuing unresolved compliance issues
- There are unexpected AE/SAE or subject safety concerns noted
- There are any unexpected inconsistencies with study product management
- There is a request for more frequent monitoring by the site
- Any mutually agreeable situation as determined by the sites and Medline

The frequency of routine monitoring may be increased to a longer interval after three monitoring cycles if on-site situations support this change. CRA will discuss this with Medline Director or Clinical Manager and will inform the PI prior to implementation.

Monitoring activities will include subject eligibility, source data review, CRF completion verification, product accountability, site continued suitability, PI study oversight, compliance, and all general monitoring activities as outlined in FDAs Code of Federal Regulations and ICH/GCP guidelines that guide that activity.

Medline Industries LP may, on occasion, contract with external Clinical Research Organizations to provide CRA services and those CRAs are authorized to act on behalf of Medline Industries, LP.

It is expected that the site will be compliant with any institutional Standard Operating Procedures during the execution of the protocol and evidence of that compliance should be readily documented and verifiable by the CRA.

The CRA will generate an internal Medline Industries LP visit report that will be filed with the Medline Industries, LP trial master file and will provide the PI a detailed follow-up letter after each monitoring visit that will outline the completed monitoring activities as well as any identified areas of concern and the expected/applicable corrections needed. Medline

Industries LP, reserves the right to perform audit of the study activities – either routine or for-cause – as needed, and may also perform clinical monitoring audit as well.

9.2 Regulatory and Ethical Considerations

9.2.1 Confidentiality and Privacy

Participant confidentiality and privacy is strictly held in trust by the investigators, their staffs, and the Sponsor. Therefore, documentation, data, and all other information generated will be held in strict confidence. No information concerning the study or the data will be released to any unauthorized third party without prior written approval of the Sponsor. All study data and study records will be managed and stored in accordance with the site's HIPAA compliant policies on data storage and security. All electronic transmission of data will adhere to HIPAA Security Rules.

The study monitor, other authorized representatives of the Sponsor, representatives of the IRB and regulatory agencies may inspect all documents and records required to be maintained by the investigators, including but not limited to, medical records (office, clinic, or hospital) and pharmacy records for the participants in this study. The clinical study sites will permit access to such records.

A master list linking subject numbers to subject name and medical record number will be maintained in a secure database (paper or electronic) by the site investigators. The study participant's contact information will be securely stored at each clinical site for internal use during the study. At the end of the study, all records will continue to be kept in a secure location for at least a period of two years, or longer if dictated by the reviewing IRB, Institutional policies, Sponsor requirements, or ICH/GCP and FDA requirements. The PI will agree to notify Sponsor of any intent to move or destroy these documents.

Study participant research data, which is for purposes of statistical analysis and scientific reporting, will be maintained at the research sites on the CRFs. Copies of the CRFs, which will not contain any identifiable information, will be provided to the Sponsor for the purposes of data analysis. The study data entry and study management systems used by clinical sites and by Medline Industries, LP research staff will be secured and stored in an access controlled locked area (any paper forms) and password protected (electronic records). At the end of the study, all study databases that are not already de-identified will be de-identified and archived at Medline Industries, LP.

9.2.2 Safety Oversight

Given that this is a post-market study on dressings used in accordance with its labeling, there is minimal safety risk to participants. The site investigators treat patients with venous ulcers and are qualified to provide adequate safety oversight for the study. In the event there are any AEs or SAEs, the site investigator will review them and make any necessary safety determinations as needed.

9.2.3 Data Handling and Record Keeping

Data collection is the responsibility of the clinical trial staff at the site under the supervision of the PI. The investigator is responsible for ensuring the accuracy, completeness, legibility, and timeliness of the data reported.

All source documents of any kind (electronic, paper, etc.) should be completed in accordance with Good Documentation Practices (GDP) to ensure accurate interpretation of data. CRFs will be created for each subject. The CRA will verify the data entered into the CRF with the site source regardless of the type of source. The site will be responsible for developing a written process that ensures the CRA is able view the source data.

Data from the CRFs will be entered into an electronic spreadsheet via dual entry to assure no errors. Data will be transferred to and analyzed with SAS[®] for statistical analysis. SAS[®] allows for internal quality checks, such as automatic range checks, to identify data that appear inconsistent, incomplete, or inaccurate. Medline Industries, LP will be responsible for overseeing final data analysis and confirmation of results.

